3.2 Primary Study Endpoints

The primary study endpoint will be between the group (OH versus non-OH) difference in fatigue (measured with the self-reported FSS), depression (measured with the self-reported GDS), apathy (measured with the AES and NPI-Q), anxiety (measured with the GAI and NPI-Q), and cognitive impairment (measured as an average composite z-score on the neurocognitive battery).

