In this study, we propose to test if NA dysfunction is associated with depression, cognition, apathy, anxiety, and fatigue in PD. First, we will test if OH in patients with PD is associated with other aspects of NP in which the adrenergic system plays a prominent role: fatigue/arousal,

attention/cognition, and apathy/depression. We will then conduct a series of physiologic tests to elucidate the contributions of central and peripheral NA dysfunction in OH in PD, and use these results to see if NA dysfunction mediates any associations between OH and NP symptoms.

These interrelated aims will help to determine if central NA dysfunction is associated with OH in PD, and whether NA dysfunction is associated with the NP symptoms in PD. These results may lead directly to treatment trials that target the NA system with the potential to significantly improve the lives of PD patients with bothersome nonmotor symptoms.

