 - Approx 1 hour after dopamine administration
- Peripheral Nerve Testing
 - HR and BP response to DB and Valsalva
 - Vibrotactile detection thresholds
 - SCOPA-AUT survey
- Dynamic Pupillometry
 - Prior to dopamine administration
 - Approximately 60 minutes post-dopamine administration
- Neuropsychiatric and neurocognitive testing (approx. 1.5 hours in length)
- Columbia Suicide Severity Rating Scale, (Baseline)

Patients will be informed to hold dopaminergic medications on the morning of Visit 1 and adrenergic medications for at least three half-lives. After providing informed consent and meeting inclusion/exclusion criteria, subjects will be asked to complete a structured interview using a standardized questionnaire/data abstraction form to obtain demographic and clinical data. Information that the patient does not know will be obtained from the medical record and the patient's primary neurologist and entered into the standardized questionnaire/data abstraction form.

The following demographics and disease characteristics will be captured:

- Age, sex, race and ethnicity
- Income
- BMI
- Highest level of education completed
- H&Y staging
- Concomitant medications including levodopa and LDED

- Years since PD diagnosis
- Comorbidities (Charleston Comorbidity Index)
- Current and prior alcohol use
- Current and prior smoking status.

Subjects will also have their OVS done at baseline (holding AM dopamine) and then again at approximately 30 minutes and 1 hour after dopamine administration.

Neuropsychiatric and neurocognitive testing

Patients will complete on one occasion a battery of neurocognitive measures.

This will include:

- The Test of Premorbid Functioning (TOPF) , a word reading based estimate of premorbid IQ ⁷⁴
- Montreal Cognitive Assessment (MoCA) ⁷⁰
- Brief University of Pennsylvania Smell Identification Test (B-SIT) ⁷⁵
- Digit Span subtest from the Wechsler Adult Intelligence Scale – IV ⁷⁶
- Symbol Digit Modalities Test (Smith, 1968) ⁷⁷
- Trail Making Test ⁷⁸
- California Verbal Learning Test – II ⁷⁹
- Rey Complex Figure Test ⁸⁰
- DKEFS Color-Word Interference Test ⁸¹
- Phonemic and Semantic Verbal Fluency ⁸²
- Behavior Rating Inventory of Executive Function – Adult ⁸³

Patient neuropsychiatric characteristics will be assessed by having them complete on one occasion:

- The Geriatric Depression Scale (GDS) ^{84, 85}
- Geriatric Anxiety Inventory (GAI) ^{86, 87}
- Fatigue Severity Scale (FSS) ⁸⁸
- Apathy Evaluation Scale (AES) ^{89, 90}

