- Activation-Deactivation Checklist to assess arousal (AD-ACL) ⁹¹

Patients will also complete a visual analogue scale before and after yohimbine to assess for acute changes in symptoms such as anxiety, fatigue, and concentration/attention [VAS; score ranging from 0% (no symptoms) to 100% (most severe symptom possible)]. ⁹⁵

An informant (when available) will complete informant report versions of the BRIEF-A, AES, as well as the Neuropsychiatric Inventory Questionnaire (NPI-Q). ⁹²

The total time for neurocognitive and neuropsychiatric testing will be approximately 1.5 hours.

Peripheral nerve testing:

This following peripheral nerve testing will performed by trained autonomic technicians and interpreted by the PI or a sub-I.

- HR and continuous BP variability monitoring with deep breathing and Valsalva.
- Patients will answer a validated survey to quantify their autonomic symptoms (the SCOPA-AUT).⁹³
- Measurement of vibrotactile detection thresholds.⁹⁴
- Dynamic pupillometry testing prior to subjects taking their levodopa-, and then again approximately 60 minutes after ingestion. See section 6.1 for pupillometry protocol.

7.3 Visit 2

HUT will be done first thing in the morning, since subjects will be holding their levodopa and other medications that could interfere with autonomic testing. Subjects will fast and abstain from coffee the morning of testing but will be encouraged to hydrate exuberantly.

[figure not shown]
Prior to beginning the HUT, the following will occur:

- Collection of adverse events since consent was signed /changes in medical history
- Collection of changes in concomitant medication will be collected.
- A C-SSRS, (Since Last Visit), will be also be performed.
- Urine pregnancy test will be performed prior to starting the HUT, (if a women is of childbearing potential,).

The following procedures will be performed as part of the HUT and measured per HUT protocol^{6, 22}, while under the supervision of a cardiac electrophysiologist, cardiology nurse and study coordinator.

- IV will be placed per standard HUT procedure.
- After approximately 30 minutes of supine rest:
 - Serum AVP and NE levels draw for baseline level
 - VAS scale completion for baseline/resting anxiety, fatigue and mood, ([VAS; score ranging from 0% (no symptoms) to 100% (most severe symptom possible)]⁹⁵).
- Pupillometric evaluations (see Figure 2).
- Tilt table to approximately 60 degrees for approximately 15 minutes; return to supine
- Yohimbine administration

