8.2 Statistical Methods

Primary analysis plan:

To test whether OH correlates with the nonmotor symptoms of fatigue, anxiety, depression, apathy, and cognitive impairment, we will compare these variables between the PD (+OH) group to the PD (-OH) group using the Mann-Whitney *U* test. Although this pilot study is likely underpowered for additional analyses, we will then construct several linear regression models with each nonmotor variable as an outcome, and also include important clinical (e.g. disease duration, total LDED) and demographic variables in the models in order to test if OH is independently associated with these nonmotor outcomes.

Secondary analysis plan:

To test whether central NA dysfunction is involved in these nonmotor symptoms, we will correlate each variable (i.e. quantified scores of depression, apathy, anxiety, fatigue, and cognition) with the difference before and after yohimbine in the change in catecholamine and AVP levels supine and at 60 degree tilt. We will also correlate the nonmotor scores with pupillary redilation speed, which measures sympathetic function, before and after yohimbine. We will compare change in anxiety, mood, and fatigue scores (measured on a visual analogue scale) before and after yohimbine between the PD (OH+) and PD (OH-) groups using the Mann-Whitney *U* test. We will also compare the changes in BP parameters before and after yohimbine between groups.

After these initial correlations and comparisons, we will construct linear regression models incorporating clinical and demographic variables of interest in order to test if our measures of NA dysfunction independently predict the nonmotor symptoms of PD, though we expect these analyses to be underpowered. Finally, we will test if central NA dysfunction (measured through changes in catecholamines and pupillary response to yohimbine, as above) explains the relationship between OH and the nonmotor symptoms of PD by incorporating our measures of central NA dysfunction into the linear regression models described above, and testing whether the relationship between OH and nonmotor symptoms persist.

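### Followed literally, the primary cognitive-impairment score averages in a premorbid-IQ estimate (TOPF) and a smell identification test (B-SIT)

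*Protocol*

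**What the plan says.** Section 3.2 lists cognition among the primary endpoints, as "cognitive impairment (measured as an average composite z-score on the neurocognitive battery". It names no component tests.

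Section 7.2 (Visit 1), under the neuropsychiatric and neurocognitive testing subheading, states: "Patients will complete on one occasion a battery of neurocognitive measures". Eleven bullets follow: TOPF, MoCA, B-SIT, Digit Span, Symbol Digit Modalities, Trail Making, CVLT-II, Rey Complex Figure, DKEFS Color-Word Interference, verbal fluency and BRIEF-A. The TOPF bullet describes the test as "a word reading based estimate of premorbid IQ". The third bullet is the "Brief University of Pennsylvania Smell Identification Test (B-SIT"). The mood, anxiety, fatigue, apathy and arousal scales form a separate list, which contains neither TOPF nor B-SIT.

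Section 1.1 says the study will "test if NA dysfunction is associated with depression, cognition, apathy, anxiety, and fatigue in PD". Smell is not in that list.

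Section 8.2 compares the cognition variable between the two groups with the Mann-Whitney test. It then uses it as a regression outcome and correlates it with the responses to yohimbine. It does not redefine the score.

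**The concern.** An average over a battery takes in whatever the battery holds. A premorbid estimate describes ability before the disease, so it is not a measure of current impairment. A smell test measures another function, and one that the protocol does not list among the outcomes it will study. With both in the average, the score no longer matches its label.

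Two things can go wrong. If neither TOPF nor B-SIT differs by OH status, they pull a true cognitive difference towards zero. If one of them does differ, that difference counts towards a result reported as cognitive impairment. Because section 8.2 carries the same cognition score forward, the problem would also reach the regressions and the correlations with the yohimbine responses.

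**Working it through.** **Text check.** Section 3.2 refers to the neurocognitive battery as a single known thing, and section 7.2 supplies the only list that fits. TOPF is bullet 1 of 11 and B-SIT is bullet 3. Sections 3.2, 7.2 and 8.2 contain no sentence that restricts the average, gives TOPF another role or sets B-SIT apart.

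**No plan figure to reproduce.** The protocol gives no effect size or power for cognition. The 4 per group in section 8.1 concerns a fatigue visual analogue scale.

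**Share of the score.** With one equally weighted score per instrument, the share is 2/11 = 0.182. If the "Phonemic and Semantic Verbal Fluency" bullet gives two scores, it is 2/12 = 0.167.

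**Effect on the raw difference.** The composite difference is the sum of weight × item difference.
- Nine items differ by *d*, two by zero: 9*d*/11 = 0.818*d*. For an assumed *d* = 0.80 SD this is 0.655 instead of 0.80.
- No cognitive difference, B-SIT differs by *s*: *s*/11. For an assumed *s* = 1.5 SD the cognitive score differs by 0.136 although cognition does not.

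**Effect on the standardised difference.** For *k* scores with common correlation ρ, the SD of the average is √((1 + (k−1)ρ)/k). Assume ρ = 0.5 throughout:
- Nine items: SD = √(5/9) = 0.745, and 0.80/0.745 = 1.07.
- Eleven items, two with no difference: SD = √(6/11) = 0.739, and 0.655/0.739 = 0.89.

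Two-sided t-test power at 11 against 11 goes from about 67% to 51%. With ρ among the nine items between 0.3 and 0.7, and the two extra items correlated between 0 and 0.5 (never above ρ), the standardised effect falls by about 2% to 17%.

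**Simulation with the planned test.** The test is the exact two-sided Mann-Whitney with 11 per group (reject if U ≤ 30 in either direction, size 0.0473). I ran 40,000 trials per scenario under a one-factor model with inter-test correlation *r* = 0.2, 0.4 and 0.6, equal weights and all scores aligned. The comparison is 8 performance tests against those 8 plus TOPF and B-SIT; BRIEF-A is left aside. The 8-test composite is set to differ by an assumed 1.3 SD, so each test differs by 1.3√((1+7r)/8) = 0.71, 0.90 and 1.05. TOPF loads on the common factor. B-SIT is independent of it unless stated.

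| Scenario | Rejection rate |
|---|---|
| 8 tests only | about 80% |
| Both added, neither differs | about 70% |
| Same, B-SIT correlated with cognition | about 61–64% |
| TOPF 0.5 SD higher in the OH group | about 61–64% |
| TOPF 0.5 SD lower in the OH group | about 74–77% |
| Smell worse by 0.8 SD in the OH group | about 77–81% |
| Smell worse by 1.5 SD in the OH group | about 83–88% |
| No cognitive difference, smell differs by 0.8 SD | about 5–6% |
| No cognitive difference, smell differs by 1.5 SD | about 6–10% |

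The direction changes with the scenario, and the documents do not say which scenario applies.

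**The case against.** The strongest reply is that this reads an instruction into silence. No sentence says that TOPF or B-SIT enters the z-score. Section 7.2 describes what patients complete, and it introduces the list as what the battery will include, which is not a closed scoring definition. An analyst who saw an endpoint called cognitive impairment beside a test described as premorbid might well leave the TOPF out. Component scores are often settled in an analysis plan, which may exist. The study is also an exploratory pilot, and section 8.1 admits that power may be short.

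Much of this is fair, and it is why the point holds only on a literal reading of two sections together. It does not remove the point. Weights, scoring direction and the z-score reference can wait for an analysis plan. Here, though, the protocol has already stated an averaging rule and the contents of the battery, so dropping two instruments later would change a primary endpoint as written.

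Three stronger readings are tempting and are not supported:
- **That the protocol bars TOPF as a covariate.** Section 8.2 will "include important clinical (e.g. disease duration, total LDED) and demographic variables in the models". The covariates named are examples, so premorbid ability is not ruled out.
- **That the primary comparison is shown to lose power or inflate false positives.** Every such figure rests on assumed inputs, power can move either way, and the false-positive effect of smell alone is small.
- **That BRIEF-A is misplaced in the same way.** It is a rating rather than a performance test, but it concerns executive function. How it is handled is detail that an analysis plan may settle.

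**Conclusion.** The point stands as a badly fixed endpoint definition. Taken literally, sections 3.2 and 7.2 put one premorbid estimate and one smell test into the primary cognitive-impairment score. The count of 2 in 11 comes from the text. The 18% share assumes one equally weighted score per instrument.

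The established harm is to interpretation: a result on this endpoint, positive or negative, could not be read as being about current cognition alone. The effect on power is not established. The drop from about 80% to 70% holds only if neither instrument differs by OH status, under the assumed 1.3 SD difference and the one-factor model; other plausible inputs give more or less. The definition should be corrected, but this does not threaten the study as a whole, because the individual scores are collected and the composite can be formed without these two.

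**What to change.** In section 3.2, restrict the composite to the battery's tests of current cognition and state that TOPF and B-SIT are excluded. Report B-SIT separately. In section 8.2, say that TOPF may be used as a premorbid-ability covariate in the regressions, which the present text already permits. Make the change before the groups are compared, so that the choice of components cannot be linked to the results.

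The cost is wording only; no test, visit or patient is added. There is one small downside: if smell really differs by OH status, the power it would have added to the composite is given up. In the simulated 1.5 SD case that is 83–88% with both instruments included against about 80% without them, but the gain would have come from smell and not from cognition.

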3.3 Secondary Study Endpoints

Secondary study endpoints will be:

- Difference between OH and non-OH group in change in supine and orthostatic catecholamine and AVP levels before and after yohimbine administration
- Difference between OH and non-OH group in change in time to pupillary redilation before and after yohimbine
- Change in self-reported anxiety, mood and fatigue before and after yohimbine
- Between group difference in baseline BP rise with yohimbine administration
- Difference in time to recovery of BP after 60 degree HUT before and after yohimbine administration
- Correlation between sympathetic function (measured with pupillary redilation and beat-to-beat BP) and levodopa use

4 Subject Selection and Withdrawal

4.1 Inclusion Criteria

1. Participant able to provide informed consent
2. Diagnosis of Parkinson's disease confirmed by a DH neurologist according to Movement Disorder Society criteria, with the exception that "Red flag" 5a will not be used (severe autonomic failure within five years of disease onset).⁶⁸
3. All subjects must have CMP and CBC drawn within 6 months of study visit 1, with results in the normal range or with abnormal results not considered to be clinically significant in the investigator's opinion. If CMP, CBC have not been drawn within 6 months of study enrollment, they will be ordered, drawn and reviewed for abnormalities of clinical significance as part of the screening process.
4. Female patients must be post-menopausal (at least one year) or have undergone surgical sterilization or hysterectomy at least 3 months before Visit 1. Women of childbearing potential must not be breastfeeding, have a negative pregnancy test at study entry and prior to yohimbine administration, have no intention to become pregnant during the course of study participation, and use contraceptive drugs or devices for the two weeks prior to and after yohimbine administration. Male patients with partners of child-bearing potential, must agree to use adequate contraception for 2 weeks before and after yohimbine administration. Adequate contraception includes oral, transdermal, or injectable (depot) estrogen and/or progestogen, selective estrogen receptor modulator therapy, intrauterine contraceptive device, double barrier method (e.g., condom and diaphragm or spermicidal gel) or vasectomy.

4.2 Exclusion Criteria

1. Diagnosis or previous history of diabetes of any kind
2. Known autonomic neuropathy unrelated to PD
3. History of or current cardiac, liver or renal disease that, in the opinion of the investigator, may put the patient at risk because of participation in the study
4. Known condition that in the investigator's opinion would be a contraindication to HUT testing or yohimbine challenge (e.g. decompensated cardiac disease, severe positional vertigo; severe anxiety, known panic disorder⁶⁹)
5. Current use of catecholaminergic medications (e.g. stimulants, droxidopa, midodrine) that cannot be held for at least three half-lives
6. Inability to hold PD medications for at least 12 hours
7. History of major depressive or bipolar disorder preceding the diagnosis of PD,⁶⁹ or diagnosis or previous history of psychiatric illness that in the investigator's opinion would affect the subject's ability to successfully participate in the study.

8. Any history (other than PD) that could affect neurocognitive function, such as history of traumatic brain injury (head injury with loss of consciousness > 1 hour), known dementia unrelated to Parkinson's or related diseases; developmental delay, multiple sclerosis, epilepsy, intellectual deficit, diagnosed and untreated sleep apnea; untreated syphilis; HIV; or other conditions that, based on the investigators opinion, could interfere with neurocognitive evaluation.
9. Known ophthalmologic disease such as untreated cataract, glaucoma, optic neuritis, orbital trauma, or other neuroretinal disease that might impact pupillary function
10. Severe illness within 30 days prior to enrollment.
11. Use of opiate, procholineric, or other medications influencing pupillary function that cannot be held for three half-lives
12. In the Investigator's opinion, subject would be unable to successfully participate in the study for any reason.

4.3 Subject Recruitment and Screening

Participation in this research requires informed consent according to Institutional Review Board (IRB) guidelines. A signed IRB approved Consent Form is the means of documenting this understanding. Subjects must be able to consent for themselves to be able to participate in this study and have received an exact copy (at point of signature acquisition). Potential recruits are instructed that their participation is voluntary and that their medical care will not be altered in any way should they elect not to participate.

Initial recruitment will take place during routine clinic visits with a DH neurologist caring for patients with PD. The study will be briefly described to the patient. If the patient is interested, a study coordinator will contact them to explain the study in detail and confirm eligibility. Interested subjects will then be sent informed consent information (i.e. study procedure, risks, and benefits) to review at home, and they will have the opportunity to ask questions prior to scheduling the first study visit. Completion of the informed consent process will then take place face-to-face at the onset of Study Visit 1, prior to any data collection. Data regarding the subject's UPDRS, H&Y standing and OVS will be gathered from the subject's medical record after consent has been obtained. All study visits and procedures will take place at Dartmouth-Hitchcock Medical Center, Lebanon, NH.

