3.1 General Design

This is a cross-sectional pilot study comparing 11 PD patients with OH to 11 PD patients without OH. OH will be defined as a drop in systolic BP of ≥ 20 mmHg or diastolic BP ≥ 10 mmHg within 5 minutes of standing (measured at 1, 2, and 5 minutes).^{59, 67} The study will include two clinical visits and a follow-up phone call 24-72 hours after the 2nd visit. Visits will last approximately 4-5 hours each. After consent has been signed, data from prior neurological exams, such as the H&Y staging, orthostatic vital signs (OVS) and UPDRS scores will be collected from a subject's medical record as part of study data.

For visit 1, subjects will be required to hold levodopa and other dopaminergic PD drugs on the morning of the visit, and other adrenergic medications for at least three half-lives. Subjects will bring their AM dopaminergic doses to be taken at the visit at the direction of study staff in order to coincide with the timing of procedures. Visit 1 will consist of reviewing informed consent and inclusion/exclusion criteria. The PI will confirm eligibility, (women of childbearing potential will undergo a serum pregnancy test as part of this eligibility review). Demographics, medical history, history and current use of alcohol, current and prior smoking status, and concomitant medications will be recorded. HR and BP response to deep breathing (DB) and Valsalva maneuvers, and vibrotactile detection thresholds, will also be tested. The subject will also undergo neurocognitive testing and neuropsychiatric assessments. OVS will be taken before administration of the subject's dopaminergic medications, and at approximately 30 minutes and 1 hour after dopamine administration. Dynamic pupillometry will be evaluated before and approximately 1 hour after administration of the subject's dopaminergic medications. If the subject has not had a CBC and CMP in the past 6 months, the PI will order and review these blood levels for any clinically significant abnormalities. This visit will last approximately 4-5 hours.

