5.4 Subject Compliance Monitoring

Subjects will be asked to hold dopaminergic medications on the morning of Visits 1 and 2 and adrenergic medications for at least three half-lives on the mornings of Visit 1 and 2. If subjects do not comply with this, the visit will be rescheduled.

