5.5 Prior and Concomitant Therapy

As part of each study visit, concomitant medications will be recorded and then reviewed. Subjects will be asked to hold levodopa and other dopaminergic medications for the morning of Visits 1 and 2. In addition, subjects may have to wean off or hold medications that interfere with autonomic testing and pupillary testing for Visits 1 and 2. Examples of medications that affect the NA axis and would have to be held for at least three half-lives include pyridostigmine, midodrine, stimulants (e.g. methylphenidate), venlafaxine, or droxidopa. This will be done with the guidance of their primary neurologists, with potential risks explained prior to patients agreeing to participate in this study. Subjects will only be enrolled if their primary neurologist feels that holding a medicine would represent minimal risk.

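### Signed consent is completed only at the onset of Visit 1, after the study-directed medication hold (for some, a wean) that Visit 1 requires

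*Protocol*

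**What the plan says.** Section 4.3 sets out recruitment in steps: the study is mentioned at a routine clinic visit, a coordinator explains it in detail, and consent information goes home. Patients are told that "they will have the opportunity to ask questions prior to scheduling the first study visit". The section then says: "Completion of the informed consent process will then take place face-to-face at the onset of Study Visit 1, prior to any data collection". It also fixes what counts as the record of consent: "A signed IRB approved Consent Form is the means of documenting this understanding". The schedule in Section 7.1 marks informed consent at Visit 1 and nowhere earlier.

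On medication, Section 3.1 says: "For visit 1, subjects will be required to hold levodopa and other dopaminergic PD drugs on the morning of the visit". The same section extends the hold to other adrenergic drugs, for at least three half-lives, and describes the visit itself thus: "Visit 1 will consist of reviewing informed consent and inclusion/exclusion criteria". Section 7.2 repeats the hold instruction. Section 5.5 adds that "subjects may have to wean off or hold medications that interfere with autonomic testing and pupillary testing for Visits 1 and 2". Section 5.4 enforces the hold: "If subjects do not comply with this, the visit will be rescheduled".

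Section 1.6 requires informed consent before research participation, presents the hold as something participation demands, and says that agreement to the dopaminergic hold is given within the consent process.

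**The concern.** A hold or wean ordered for the study is not part of the patient's care. If it happens before the form is signed, the patient has taken on a study risk without the documentation that the protocol itself specifies.

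The stake is greatest for users of adrenergic drugs. Section 1.6 names sleepiness, mild hypotension, anxiety, agitation and sweating among the possible effects of stopping them, and 11 of the 22 planned subjects are selected because they have orthostatic hypotension. A patient who declines at the onset of Visit 1, or whom the investigator finds ineligible there, has already been through the whole Visit 1 hold. This is a matter of subject protection; nothing here changes an endpoint or an analysis.

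**Working it through.** The point rests on the order of events, so the main check is to set the sections side by side. The plan states no figure to reproduce.

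**Order of events as written**

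1. Clinic mention, coordinator's explanation, consent information sent home, questions taken, Visit 1 scheduled (Section 4.3). Nothing is signed.
2. Adrenergic drugs held for at least three half-lives, or weaned in some patients (Sections 3.1, 5.5, 7.2).
3. Dopaminergic drugs held on the morning of the visit (Sections 3.1, 5.4, 7.2). Subjects bring their morning doses to take later under staff direction, so they arrive off drug.
4. Arrival at Visit 1. If the hold was not done, the visit is rescheduled (Section 5.4).
5. Consent completed and signed; eligibility confirmed (Sections 3.1, 4.3).
6. Baseline assessments off medication.

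Steps 2 and 3 precede step 5 for every subject who follows the instructions.

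**Comparison with the protocol's own rules**

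- Section 1.6 requires consent before research participation and makes the hold a requirement of participation. With the signature at step 5, the documented consent follows that requirement instead of preceding it.
- Section 1.6 places agreement to the dopaminergic hold inside the consent process. Section 4.3 completes that process only after the first such hold.
- Section 12 requires formal consent, on the approved form, before any study procedure. The protocol does not call the hold a procedure, so this conflict exists only if the hold is read as one. The conclusion does not need that reading.

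**Size**

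- Planned subjects: 11 + 11 = 22 (Section 3.1). If every subject takes a dopaminergic drug (an assumption), up to 22 hold it before signing, for one morning.
- Users of adrenergic drugs: not stated, so the range is 0 to 22.
- Drug remaining after three half-lives, assuming first-order elimination: 0.5³ = 0.125, or 12.5%. A user who has held for at least that long has therefore completed at least 1 − 0.125 = 0.875, or 87.5%, of the washout before signing. This only restates the three-half-life rule; it shows that the hold is essentially complete by signature and does not measure harm.

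**The case against.** The strongest reply is that consent here is a process and that patients are not uninformed. The coordinator explains the study, written information on procedures, risks and benefits goes home, and questions are taken before scheduling. Sections 1.6 and 5.5 also say that the risks of holding or weaning are explained before a patient agrees to take part, under the primary neurologist's guidance, and Section 5.5 adds: "Subjects will only be enrolled if their primary neurologist feels that holding a medicine would represent minimal risk". The dopaminergic hold is short and rated minimal risk. The protocol does not list the hold among its procedures, and Section 4.3 places study procedures at the medical center. Its own rule of consent before data collection is met. Yohimbine is given only at Visit 2, well after signature. Face-to-face signing has merit in a population whose cognition is under study, and the removed consent pages could describe an arrangement that cannot be seen here.

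Much of this stands. It narrows the problem from uninformed holds to late documentation, and it makes Section 12 a conditional conflict at most. It does not supply a signed form before the hold, and Section 4.3 names that form as the means of documentation. Whether or not the hold is labelled a procedure, Section 1.6 ties it to participation and puts consent first. The merit of face-to-face consent is kept if consent is re-confirmed in person at Visit 1.

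**Conclusion.** The concern holds. As written, documented consent follows a study-directed and enforced medication change, contrary to the order that Section 1.6 sets. The deficiency is mainly one of documentation, because information, time for questions and neurologist approval all come earlier.

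Its reach is up to 22 subjects for a one-morning dopaminergic hold of minimal stated risk, assuming all take such drugs, and an unstated number (0 to 22) for the longer adrenergic hold or wean, where the named risks are more substantial. The conclusion depends on the sequence in Sections 3.1, 4.3, 5.4, 5.5 and 7.2 and not on the washout arithmetic. It should be corrected, but it does not threaten the study's results.

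**What to change.** Amend Sections 4.3 and 7.2, with matching changes to Section 3.1 and the schedule in Section 7.1, so that the form is signed after the coordinator's explanation and home review and before any study-directed hold or wean begins. Signature could be remote or by mail if the IRB allows, otherwise at one short contact. Re-confirm consent face-to-face at the onset of Visit 1. The hold itself need not change.

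The cost is an IRB amendment and an earlier signature step. Because consent information already goes home and questions are already taken before scheduling, no extra visit is needed where remote or mailed signature is permitted.
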